5.3 Prohibited Medications and Therapy

During the study all other investigational drugs are prohibited. In addition, the following drugs are prohibited.

JAK Inhibitors

Concomitant use of JAK inhibitors (including but not limited to ruxolitinib [Jakafi®], tofacitinib [Xeljanz®], baricitinib, upadacitinib, and filgotinib).

Corticosteroids

- Intravenous (IV), intramuscular (IM) and epidural corticosteroids
- Intra-articular, trigger point or tender point, intra-bursa, and intra-tendon sheath corticosteroids are exclusionary and NOT allowed in Period 1 up to Week 36 unless a subject qualifies for rescue therapy at the Week 16 visit;
- Oral corticosteroids (refer to Section 5.1 Eligibility Criterion 31 for more information).

Biologic Therapies

All concomitant biologic therapies and biosimilars versions of biologic drugs for the treatment of PsA are prohibited during the study (Period 1 and Period 2). Examples of biologic therapies include but are not limited to the following:

- Humira® (adalimumab)
- Enbrel® (etanercept)
- Remicade® (infliximab)

- Orencia® (abatacept)
- Cimzia® (certolizumab pegol)
- Simponi® (golimumab)
- Stelara® (ustekinumab)
- Taltz® (ixekizumab)
- Cosentyx® (secukinumab)
- Tremfya® (guselkumab)

Opiates

Opiates, with the exception of tramadol, codeine, or hydrocodone, alone or in combination with acetaminophen, are not permitted during the study and subjects must have discontinued at least 1 week prior to the first dose of study drug.

Opiates including (but not limited to):

- buprenorphine
- fentanyl
- hydromorphone
- levophanol
- meperidine
- methadone
- morphine
- oxycodone
- oxymorphone
- propoxyphene

Vaccines

Live vaccines are not permitted during study participation including up to 140 days (20 weeks) after the last dose of study drug. Although not mandated by the protocol, it is recommended that subjects be up to date on vaccines recommended by local guidelines. If the subject and investigator choose to administer live vaccines, these vaccinations must be completed at least 6 weeks before first dose of study drug.

Examples of live vaccines include, but are not limited to, the following:

- Monovalent live attenuated influenza A (H1N1) (intranasal)
- Seasonal trivalent live attenuated influenza (intranasal)

- Herpes zoster (Zostavax®)
- Rotavirus
- Varicella (chicken pox)
- Measles-mumps-rubella or measles mumps rubella varicella
- Oral polio vaccine
- Smallpox
- Yellow fever
- Bacille Calmette-Guérin (BCG)

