5.5 Withdrawal of Subjects and Discontinuation of Study

Lack of response within the context of this study is defined as not achieving at least a 20% improvement in either or both TJC and SJC, compared to Baseline, on 2 consecutive visits. This evaluation begins at Week 32; therefore, Week 36 is the first possible time point a subject might be discontinued for lack of response. From Week 36 onward, study subjects will continue to be evaluated for lack of response on two consecutive visits. Discontinued subjects will be followed through the remainder of the study.

A subject may voluntarily withdraw or be withdrawn from the study or study treatment at any time for reasons including, but not limited to, the following:

- Clinically significant abnormal laboratory result(s) or AEs, which rule out continuation of the study drug, as determined by the Investigator or the AbbVie Therapeutic Area Medical Director (TA MD) (as applicable).
- The Investigator believes withdrawal from the study treatment or study is in the best interest of the subject.

- The subject requests withdrawal from the study treatment or study.
- Eligibility criteria violation(s) are noted after the subject started study drug, if continuation of the study drug would place the subject at risk as determined by the AbbVie TA MD, after consultation with the investigator.
- Subject needs to initiate prohibited medication(s) or dosages, and continuation of the study drug would place the subject at risk as determined by the AbbVie TA MD.
- The subject becomes pregnant while on study drug.
- Subject is non-compliant with TB prophylaxis (if applicable) or develops active TB at any time during the study (see Operations Manual, Section 3.12).
- Subject is diagnosed with a malignancy (Exception: localized non-melanoma skin cancer or carcinoma in-situ of the cervix, where continuation of the subject is at the discretion of the investigator).
- Subject is significantly non-compliant with study procedures which would put the subject at risk for continued participation in the trial as determined by the Investigator or AbbVie TA MD.
- Occurrence of following hepatic test abnormalities that is confirmed on a separate sample following a repeated blood draw:
 - ALT or AST $> 8 \times$ Upper Limit of Normal (ULN);
 - ALT or AST $> 5 \times$ ULN for more than 2 weeks;
 - ALT or AST $> 3 \times$ ULN and (Total Bilirubin $> 2 \times$ ULN or international normalized ratio [INR] > 1.5);

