5.6 Follow-Up for Subject Withdrawal from Study

To minimize missing data for efficacy and safety assessments, subjects who prematurely discontinue study drug treatment should continue to be followed for all regularly scheduled visits, unless subjects have decided to discontinue the study participation entirely (withdrawal of informed consent).

Subjects who prematurely discontinue study drug should complete a Premature Discontinuation Visit (PD Visit) as soon as possible. Afterwards, subjects should follow the regular visit schedule as outlined in the Activity Schedule ([Appendix D](#)) and adhere to all study procedures except for dispensing study drug, pharmacokinetic (PK) sample collection, and biomarker sample collection for optional exploratory research. Once the subject has discontinued study drug, all rescue- and efficacy-driven discontinuation criteria no longer apply. If at any point a subject no longer wants to provide assessments (withdrawal of informed consent) following discontinuation of study drug, a second PD visit is not required.

If a subject prematurely discontinues study participation but is willing to receive a 140-day (20-week) follow-up phone call after the last dose of study drug, the phone call should be completed to ensure all treatment-emergent AEs/serious AEs (SAEs) have been resolved. The follow-up phone call will not be conducted for subjects who withdraw study consent.

All attempts must be made to determine the primary reason for discontinuation of study drug or study participation. The information will be recorded on the appropriate eCRF page. However, these

procedures should not interfere with the initiation of any new treatments or therapeutic modalities that the Investigator feels are necessary to treat the subject's condition. Following discontinuation of study drug, the subject will be treated in accordance with the Investigator's best clinical judgment, irrespective of whether or not the subject decides to continue participation in the study. Subjects who prematurely discontinue from the study will not be replaced.

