7.3 Prior and Concomitant Medications

Prior and concomitant medications will be summarized by generic name. A prior medication is defined as any medication taken prior to the date of the first dose of study drug (risankizumab or placebo). A concomitant medication is defined as any medication that is started prior to the date of the first dose of study drug and continues to be taken after the first dose of study drug or any medication that is started on or after the date of the first dose of study drug and not after the date of the last dose of study drug + 140 days. The number and percentage of subjects taking medications will be summarized by generic drug name based on the World Health Organization (WHO) Drug Dictionary for both prior and concomitant medications. In addition, the number and percentage of subjects taking rescue medication will be summarized by ATC classification level 2, generic drug name and route of administration. A listing of subjects taking rescue medication with generic drug name, dosage and route of administration will also be provided.

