8.0 Efficacy Analyses

8.1 General Considerations

All efficacy analyses will be conducted in the FAS Population. In addition, Per-protocol analysis for primary endpoint will be performed. All tests will be 2-sided at an alpha level of 0.05.

The Primary Analysis will be conducted after all ongoing subjects have completed Week 24 and the Week-24 Database Lock has occurred. Efficacy and safety analyses will be performed for Period 1 and long-term efficacy and safety will be summarized through the data cutoff date. An additional interim database lock will be conducted to provide further efficacy and safety exposure for integrated summaries of efficacy and safety supporting the initial regulatory submission; no study-specific analysis will be performed based on this database lock.

Unless otherwise specified, categorical variables will be analyzed using Cochran-Mantel-Haenszel (CMH) test, adjusting for the stratification factors. Continuous variables will be analyzed using Mixed-Effect Model Repeat Measurement (MMRM) method.

Unless otherwise specified, any subject who is randomized based on a wrong stratum will be analyzed according to the actual stratum the subject belongs to.

"Baseline" refers to the last non-missing observation before the first administration of study drug or before randomization if no study drug is given.

Efficacy analysis for Period 1

The efficacy analysis for Period 1 will be performed after all ongoing subjects have completed Period 1 and an interim database lock has occurred. This is the only and final efficacy analysis in Period 1.

Long-term efficacy analysis

Long-term efficacy will be summarized based on data in Period 1 and Period 2 up to data cutoff date for the Week-24 Database Lock. After the initial regulatory submission, additional interim analyses will be performed as deemed appropriate, for example, to address requests from regulatory agencies. The final analysis will be performed after all ongoing subjects complete the study.

The long-term efficacy analysis will be performed on As Observed data (defined in Section 8.2) by randomized treatment group sequence as described below:

1. Placebo → risankizumab 150 mg
2. risankizumab 150 mg → risankizumab 150 mg

There will be no statistical testing for long-term efficacy analysis; only descriptive statistics and 95% confidence intervals will be provided.

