The AO analysis will not impute values for missing evaluations, and thus a subject who does not have an evaluation on a scheduled visit will be excluded from the AO analysis for that visit. Regardless of premature discontinuation of study drug, initiation of concomitant medications for PsA use that could meaningfully impact efficacy assessment,

or initiation of rescue medication, all observed data will be used in the analysis. The AO analysis will be used to facilitate the supplementary analysis.

AO with Imputation

The AO with imputation will use all observed data regardless of premature discontinuation of study drug, initiation of concomitant medications for PsA use that could meaningfully impact efficacy assessment, or initiation of rescue medication and will impute missing as non-responders. It will be used for the supplementary analysis for binary variables.

Multiple Imputation (MI)

As a sensitivity analysis, MI will be utilized for both hypothetical and treatment policy estimand ([Appendix D](#)). MI analysis will be performed based on AO data. The MI analysis will impute missing data multiple times under appropriate random variation and thus generate multiple imputed "pseudo-complete" datasets. SAS PROC MI will be used to generate 30 datasets using the fully conditional specification (FCS) method. Specifically, treatment group is included in the FCS imputation model to enable stratified sampling. Additionally, the imputation model includes demographics variables, baseline disease characteristics, stratification factors, as well as longitudinal response observed at any other visits. Analysis using CMH for binary endpoints and analysis of covariance (ANCOVA) for continuous endpoints will be performed on each of the multiple imputed datasets. Subsequently SAS PROC MIANALYZE will then be used to aggregate the results for the final statistical inference using Rubin's method.¹

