8.5 Additional Efficacy Analyses

Additional endpoints defined in Section 3.3 will be analyzed in at scheduled time points other than those specified for the primary and key secondary variables.

Additional Efficacy Analyses for Period 1

Additional endpoints will be analyzed for each randomized treatment group for all visits.

For binary endpoints, point estimate and 95% CI using normal approximation will be provided for the response rate for each randomized treatment group. Point estimate, 95% CI and p-value will be provided for the treatment comparison between risankizumab 150 mg and the placebo group based on the CMH test adjusting for stratification factors. Only the nominal p-value will be provided. NRI-C for missing data handling will be used. AO analysis will be used as supplementary analysis.

For continuous endpoints, the LS mean and 95% CI will be reported for each randomized treatment group. The LS mean treatment difference and associated 95% CI and p-values between risankizumab 150 mg and the placebo group will be provided using MMRM model. Only the nominal p-value will be provided. Data observed after initiation of rescue or concomitant medications for PSA that could meaningfully impact efficacy assessment will be excluded. Supplementary analysis will be conducted based on ANCOVA model using AO data, with treatment and stratification factors as the fixed factors and the corresponding baseline value as the covariates. Nominal p-values will be provided.

For HRU related endpoints, number and percentage of subjects with non-study health visits will be provided by visit and over the double-blind period up to Week 24. In addition, cumulative number of utilizations per time (e.g., subject-year) up to Week 24 will be provided for each category.

Long-Term Efficacy Analyses

Assessments to evaluate long-term efficacy will be analyzed for all efficacy measurements at scheduled visits.

Descriptive statistics will be provided for each randomized treatment sequence as defined in Section 8.1. These include the number of observations, mean, standard deviation, 95% CI, median, minimum, and maximum for continuous endpoints, and frequencies and percentages with 95% CI using normal approximation for binary endpoints. Plot for each randomized treatment group sequence over time will be provided for primary and multiplicity-controlled secondary endpoints and selected additional endpoints. These efficacy analyses will be based on AO analysis.

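### Long-term ACR response is summarised on As Observed data only, which can overstate response if subjects stopped for lack of joint response then leave the study or respond on other therapy

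*SAP*

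**What the plan says.** SAP 8.1 sets the long-term method: "The long-term efficacy analysis will be performed on As Observed data (defined in Section 8.2) by randomized treatment group sequence". SAP 8.5 repeats it: "These efficacy analyses will be based on AO analysis". SAP 10.0 plans nothing further. Under SAP 8.2, AO leaves an unassessed subject out of that visit and uses every observed value, whatever has happened to study drug, rescue or other PsA medication. For the method in general, the same section says: "The AO analysis will be used to facilitate the supplementary analysis". SAP 8.2 also defines AO with Imputation, which uses the same observed data but counts a missing value as non-response. SAP 8.3.4 and 8.4.2 assign it to the primary and secondary endpoints, and nothing assigns it to the long-term summaries.

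Protocol 5.5 stops study drug when the 20% improvement criterion for tender and swollen joint counts is failed at two visits in a row: "This evaluation begins at Week 32; therefore, Week 36 is the first possible time point a subject might be discontinued for lack of response". It adds: "Discontinued subjects will be followed through the remainder of the study". Protocol 5.6 also intends follow-up to continue but lets a subject withdraw entirely. On treatment after study drug is stopped, 5.6 says "the subject will be treated in accordance with the Investigator's best clinical judgment". Protocol 5.3 says that concomitant biologics "for the treatment of PsA are prohibited during the study (Period 1 and Period 2"), and it also bars JAK inhibitors.

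**The concern.** The stopping rule creates a group that is non-responding on ACR by construction. ACR20 in the Operations Manual (Appendix E) requires at least 20% improvement in both joint counts. Whether the stopping rule means failing one count or failing both, a stopped subject fails at least one, and so is not an ACR20, ACR50 or ACR70 responder at the qualifying visits.

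The reported long-term rate then depends on what happens to that group. Those who withdraw disappear from the AO denominator. Those who stay and respond on another PsA therapy count as responders under a risankizumab sequence. Both routes push the rate up.

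Long-term efficacy of risankizumab 150 mg is a stated secondary objective. From AO alone, a reader cannot separate maintained response on the drug from attrition of non-responders or from response to something else.

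**Working it through.** **The plan's own figures.** The documents give no long-term response rate to reproduce. Their only sizing figure is the Week 24 power in SAP 2.4. With 210 × 0.9 = 189 per arm, power is 0.90 for HAQ-DI (difference 0.24, SD 0.72) and 0.976 for ACR20 (35.7% against 55.7%), so the statement reproduces. The present point does not depend on it.

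**Inputs.** The 210 per sequence comes from the documents. The rest are assumptions:
- s, share of a sequence stopped for lack of response: 5% to 20%
- r, ACR20 response among those still on drug: 60% or 70%
- m, share of stopped subjects who leave the study
- q, later ACR20 response among stopped subjects who stay

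**Formulas.**
- AO = [(1−s)r + s(1−m)q] / (1−sm)
- Reference, stopped subjects counted as non-responders = (1−s)r
- AO with Imputation = (1−s)r + s(1−m)q

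**Results, AO against reference (%).**

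| Case | s = 5%, r = 60% | s = 20%, r = 70% |
|---|---|---|
| All stay, none responds (m=0, q=0) | 57.0 vs 57.0: 0 | 56.0 vs 56.0: 0 |
| A quarter leave (m=0.25, q=0) | 57.0/0.9875 = 57.7 vs 57.0: 0.7 | 56.0/0.95 = 58.9 vs 56.0: 2.9 |
| Half leave (m=0.5, q=0) | 57.0/0.975 = 58.5 vs 57.0: 1.5 | 56.0/0.90 = 62.2 vs 56.0: 6.2 |
| All stay, a quarter respond (m=0, q=0.25) | 57.0 + 1.25 = 58.25 vs 57.0: 1.25 | 56.0 + 5.0 = 61.0 vs 56.0: 5.0 |

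A check with the overall rate fixed at the planning value of 35% + 20% = 55% gives nearly the same answer. If half leave, AO is 55/0.975 = 56.4 (+1.4) at s = 5% and 55/0.90 = 61.1 (+6.1) at s = 20%.

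**What AO with Imputation repairs.** With q = 0 it equals the reference, so the withdrawal route closes. With m = 0 it equals AO, so response on later therapy stays in the rate and has to be shown separately.

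**Can existing outputs show it?** Only in part. SAP 5.0 gives drug discontinuation and study non-completion with reasons, but not by visit. SAP 7.3 counts a newly started medication as concomitant only if its start is "not after the date of the last dose of study drug + 140 days". A subject stopped at Week 36 had the last dose at Week 28 (Day 196), so the window closes at Day 196 + 140 = Day 336, Week 48. The (208 − 52)/12 + 1 = 14 scheduled visits from Week 52 to Week 208 all come later. AO can still count a response at those visits while the medication behind it is absent from the summary. Week 36 is the earliest stop; later stops have later windows.

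**The case against.** The strongest reply is that the excess exists only against a chosen reference. In every case above, AO is at or below r, the response among those still on drug. It is too high only as a rate for the whole sequence with stopped subjects counted as failures. The documents adopt no such long-term target: Protocol 7.3 asks for descriptive statistics, and SAP 8.2 does not list stopping drug as an intercurrent event. This stands, and it is why AO should remain and why there is no contradiction with the protocol.

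The written plan keeps stopped subjects in follow-up, and if that works and none responds later, the excess is zero. All inputs except 210 are assumed. The computed excesses are also smaller than the AO 95% half-width of 6.3 points (n = 210, rate 67.75%) to 7.4 points (n = 168, rate 60%). This stands too, although a systematic shift is not covered by a sampling interval.

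A reader might infer that every drug stop should be scored as permanent non-response. The documents do not support that. Placebo-sequence subjects first receive risankizumab at Week 24 and can be stopped at Week 36, 12 weeks later, so a later response need not come from another therapy.

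Readers can roughly bound the effect from disposition reasons and from the observed counts behind the percentages. They cannot do so by visit, nor for therapy started after the medication window closes.

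**Conclusion.** The point holds as a conditional one. AO is the only long-term method, and the protocol's stopping rule together with permitted withdrawal can raise the AO ACR rate above the rate in all subjects of a sequence. The excess is zero if follow-up holds and none responds later. It is 0.7 to 6.2 points if a quarter to half of stopped subjects leave, and 1.25 to 5.0 points if all stay and a quarter respond later. These figures rest on the assumed 5% to 20% stopped and 60% to 70% response on drug.

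Three stronger readings are not supported. One is that AO must inflate the rate, by as much as s × r = 3 to 14 points; that requires every stopped subject to leave, contrary to the follow-up plan. Another is that PASI 90 or other endpoints are overstated in the same way; the stopping rule concerns joint counts only. The third is that the main results are at risk; the long-term analysis has no testing, and the Week 16 and Week 24 comparisons use other data handling. This is a worthwhile, inexpensive improvement to a descriptive summary.

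**What to change.** In SAP 8.1 and 8.5, keep AO as planned and make two additions.

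1. For long-term ACR20/50/70 only, add a supplementary summary using AO with Imputation as already defined in SAP 8.2. Limit it to visits due by the data cutoff and state the denominator, for example FAS subjects who entered Period 2.
2. Beside it, tabulate by visit and sequence the numbers assessed, missing (COVID and non-COVID separately), off study drug, and on a PsA medication from the list of impactful medications that SAP 8.2 says will be identified before lock. Count starts at any time in follow-up, without the 140-day limit, so that response after other therapy is visible.

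Do not score the drug stop itself as permanent non-response, and do not extend the NRI-C imputation model beyond Week 24; neither is needed for this point. Separately, Protocol 5.3 and 5.6 must be reconciled on which therapies are allowed for stopped subjects who remain in follow-up.

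The cost is SAP wording and modest programming. Protocol 5.4 already has medications recorded through the last call, up to Week 228. The downside is possible understatement when visits are missing for reasons unrelated to efficacy, including COVID. For example, if 5% are missing for such reasons and true response is 60%, the added rate is 0.95 × 60 = 57.0, which is 3.0 points low. Both summaries should therefore be shown together.
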